6.9.7. Immune Response to AAV8 and G6Pase

Neutralizing antibodies to AAV8, AAV8 binding antibody IgG assay, and anti-G6Pase antibody assay will be summarized by study visit. Listings for these safety parameters will be provided. Data from both studies 401GSDIA01 and 401GSDIA02 will be included in this analysis.

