2. PROTOCOL SYNOPSIS

Name of Sponsor: Ultragenyx Pharmaceutical Inc. (Ultragenyx)

Ultragenyx Product: DTX401

Title: A Long-Term Follow-up Study to Evaluate the Safety and Efficacy of Adeno-Associated Virus (AAV) Serotype 8 (AAV8)-Mediated Gene Transfer of Glucose-6-Phosphatase (G6Pase) in Adults with Glycogen Storage Disease Type Ia (GSDIa)

Study Phase: Phase 1/2

Study Rationale:

The design of this study is consistent with global regulatory guidelines for protocol design. Study 401GSDIA02 is a long-term follow-up study to evaluate the safety and efficacy of adenoassociated virus (AAV) serotype 8 (AAV8)-mediated gene transfer of glucose-6-phosphatase (G6Pase) in adults with glycogen storage disease type Ia (GSDIa). Only subjects who received DTX401 in Study 401GSDIA01 are eligible to participate in Study 401GSDIA02. Study 401GSDIA01 was a Phase 1/2, open-label safety and dose-finding study of AAV8-mediated gene transfer of G6Pase in adults with GSDIa, during which subjects received a single intravenous (IV) dose of DTX401 with steroids (prednisone) to manage alanine aminotransferase (ALT) elevation. Overall, 12 patients were enrolled in following cohorts of 3 subjects each:

- Cohort 1: Dose 1 (2.0×10^{12} genome copies [GC]/kg) with a reactive steroid regimen (prednisone starting dose of 40 mg/day)
- Cohort 2: Dose 2 (6.0×10^{12} GC/kg) with a reactive steroid regimen (prednisone starting dose of 40 mg/day)
- Cohort 3: Dose 2 (6.0×10^{12} GC/kg) with an optimized reactive steroid regimen (prednisone starting dose of 60 mg/day)
- Cohort 4: Dose 2 (6.0×10^{12} GC/kg) with a prophylactic steroid regimen

No investigational product (IP) will be administered during Study 401GSDIA02.

Study Design:

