2.3. Tertiary Objectives and Endpoints (s)

The tertiary objectives of this study are as follows:

- To evaluate the long-term effect of DTX401 on lipid profiles (total cholesterol, low-density lipoprotein, and triglycerides)
- To evaluate the long-term effect of DTX401 on uric acid
- To evaluate the long-term effect of DTX401 on proteinuria
- To evaluate the long-term effect of DTX401 on liver size and fat content
- To evaluate the long-term effect of DTX401 on hepatic adenoma progression
- To assess the long-term impact of DTX401 on cornstarch requirements
- To assess the long-term impact of DTX401 on glucose homeostasis
- To assess the long-term impact of DTX401 on the subject's health-related quality of life (HRQoL) and sleep quality
- To describe the long-term immune response to AAV8 capsid proteins after IV administration of DTX401
- To describe the long-term immune response to G6Pase after IV administration of DTX401
- To evaluate the long-term effect of DTX401 on lactate levels

- To evaluate the long-term effects of DTX401 on the endocrine and metabolic responses to fasting

The tertiary endpoints of this study are as follows:

- Total cholesterol, low-density lipoprotein, and triglycerides, by time point, cohort, and overall
- Uric acid, by time point, cohort, and overall
- 24-hour urine protein, by time point, cohort, and overall
- The change from baseline in liver size and fat fraction (by MRI) over time following IV administration of DTX401, by cohort, and overall
- The average daily use of cornstarch (or equivalent) over time, by cohort, and overall
- Assessment of serum glucose levels over time, summarized by cohort
- Subject responses to HRQoL and sleep quality assessments over time following IV administration of DTX401, by cohort and overall
- Year 2 – Exit Interviews
- The development of neutralizing antibodies to AAV8 (as determined by a cell-based assay) over time, by cohort, and overall
- The development of anti-AAV8 binding antibodies (as determined by ELISA) over time, by cohort, and overall
- The development of anti-G6Pase antibodies over time, by cohort, and overall
- Assessment of lactate levels over time, summarized by cohort and overall

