3.6. Sample Size Considerations

The study is expected to enroll up to 12 subjects. The sample size is not based on a power calculation.

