6. STATISTICAL ANALYSIS

6.1. General Principles

All analyses in the study will be descriptive; no formal hypotheses will be tested. An integrated analysis using data from both Study 401GSDIA01 and Study 401GSDIA02 will be performed to summarize and assess the long-term safety and efficacy of DTX401; there will not be a standalone analysis of data from only Study 401GSDIA02.

Continuous variables will be summarized by number of subjects, mean, SD, standard error (SE), median, Q1, Q3, minimum, and maximum values. Categorical variables will be summarized by number and percentage of subjects. All summary tables will be presented by scheduled study visit and no analysis windows will be used, unless specified otherwise. Study visits from both studies 401GSDIA01 and 401GSDIA02 will be included in summary tables.

All summary tables will be presented by dose cohort of DTX401 (see below), Cohorts 2, 3, 4 combined (i.e., cohorts for dose 2 combined), and overall, unless specified otherwise.

The dosing cohorts are:

- Cohort 1: Dose 1 (2.0×10^{12} GC/kg) with a reactive steroid regimen (prednisone starting dose of 40 mg/day)
- Cohort 2: Dose 2 (6.0×10^{12} GC/kg) with a reactive steroid regimen (prednisone starting dose of 40 mg/day)
- Cohort 3: Dose 2 (6.0×10^{12} GC/kg) with an optimized reactive steroid regimen (prednisone starting dose of 60 mg/day)
- Cohort 4: Dose 2 (6.0×10^{12} GC/kg) with a prophylactic steroid regimen

SAS[®] software version 9.4 or higher will be used to perform statistical analyses unless otherwise specified.

Handling of missing or incomplete data is described in [Appendix 1](#).

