6.9. Safety Analysis

The safety analysis will be performed using the FAS. The safety parameters will include AEs, SAEs, vital sign measurements, physical examination findings, electrocardiogram (ECG) results, subject reported symptomatic hypoglycemic events, clinical laboratory assessments (clinical chemistry [including liver function tests], hematology, coagulation panel, and urinalysis), vector shedding, vector genome determination, measurement of neutralizing antibody titer to AAV8, measurement of AAV8 binding antibody immunoglobulin G (IgG), assessment of any cell-mediated immune responses to AAV8 and G6Pase, and measurement of anti-G6Pase antibodies.

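### SAP 6.9.7 gives the AAV8 antibody titres only a by-visit summary, with no log-scale statistic and no within-subject fold change, although the tertiary endpoint is development over time (minor; cheap to improve)

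*SAP*

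**What the plan says.** SAP 2.3 lists as a tertiary endpoint "The development of neutralizing antibodies to AAV8 (as determined by a cell-based assay) over time, by cohort, and overall", with parallel endpoints for AAV8 binding antibody and anti-G6Pase antibody. SAP 6.9 describes the neutralizing result as a titre: "measurement of neutralizing antibody titer to AAV8".

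SAP 6.9.7 is the whole analysis text for these assays: "Neutralizing antibodies to AAV8, AAV8 binding antibody IgG assay, and anti-G6Pase antibody assay will be summarized by study visit". It adds listings and the inclusion of data from both studies. It names no scale, geometric mean, fold change, change from baseline or definition of a new positive.

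The general rules in SAP 6.1 therefore apply. For continuous data: "Continuous variables will be summarized by number of subjects, mean, SD, standard error (SE), median, Q1, Q3, minimum, and maximum values". For categorical data: "Categorical variables will be summarized by number and percentage of subjects". The columns are also set there: "All summary tables will be presented by dose cohort of DTX401 (see below), Cohorts 2, 3, 4 combined", and overall. The protocol synopsis gives the cohort size: "Overall, 12 patients were enrolled in following cohorts of 3 subjects each".

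Change from baseline is named in the SAP for the fasting challenge (6.8.1), cornstarch (6.8.2), MRI (6.8.6), quality of life (6.8.7), central laboratory parameters (6.9.3) and vital signs (6.9.4). SAP 6.9.3 limits it to the parameters in SAP Table 2, which omits the antibodies.

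**The concern.** A titre is a multiplicative quantity, and whether antibodies rise, persist or fall is a question about each subject against that subject's own starting value. The planned summary addresses neither feature directly. In a column of three, the arithmetic mean and SE of raw titres can mostly describe the highest subject. A by-visit table also compares columns, not subjects.

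The second issue grows late in follow-up. Protocol Figure 2 places antibody sampling at Weeks 104, 156, 208 and 260, and subjects may move to the disease monitoring program once they have reached Week 208. If some have left by Week 260, that column holds fewer subjects, and its mean or median can shift through composition alone.

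What is at stake is how clearly the report can describe the long-term immune response. No test or trial decision depends on it.

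**Working it through.** **1. Figures in the plan.** The documents state no titre spread, effect size, alpha or power for these assays, so there is no figure to reproduce. The column sizes follow from the cohorts: 4 × 3 = 12 overall, 3 × 3 = 9 in Cohorts 2-4 combined, and 3 per cohort, all as upper limits.

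**2. Protocol against SAP.** Protocol 12.4.4 summarises absolute values and change from baseline for all clinical laboratory parameters with continuous results. Protocol Table 2 lists AAV8 neutralizing antibody, AAV8 binding IgG and anti-G6Pase antibody among the clinical laboratory parameters, in its last row. Together these call for change from baseline where the result is continuous. SAP 6.9.7 does not carry this over, and SAP section 7 declares no change from the protocol. However, protocol 12.6, the specific immunogenicity section, asks only for a summary over time.

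**3. How far one titre drives the mean.** Assume titre = 10^z with z normal and SD 0.5 or 0.8 between subjects. Share of the highest subject = largest titre / sum of titres, from 200,000 simulated columns:

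| Subjects in column | Median share, SD 0.5 | Median share, SD 0.8 | Share above half, SD 0.5 | Share above half, SD 0.8 |
|---|---|---|---|---|
| 3 | 61% | 73% | 76% | 89% |
| 9 | 35% | 49% | 17% | 48% |
| 12 | 30% | 44% | 9.5% | 39% |

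Equal titres would give 33% at n = 3. With a narrow spread (natural-log SD 0.5, about 0.22 on log10) the median share at n = 3 is 46%.

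An invented example inside the assumed range is 800, 1600 and 12800 (log10 SD 0.63):
- mean = 15200 / 3 = 5067, SE 3874
- highest share = 12800 / 15200 = 84%
- median 1600
- geometric mean = (800 × 1600 × 12800)^(1/3) = 2540

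**4. Does the summary show the right direction?** Suppose titres truly halve, with the same 9 subjects at both visits. Assume a shared subject effect with log10 SD s and independent visit error, so that the within-subject log10 change has SD d. The table gives the percentage of simulated trials in which the column statistic rises instead of falling:

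| s | d | Arithmetic mean | Median | Geometric mean |
|---|---|---|---|---|
| 0.5 | 0.30 | 2% | 4% | 0.1% |
| 0.5 | 0.45 | 9% | 10% | 2.2% |
| 0.8 | 0.30 | 5% | 7% | 0.1% |
| 0.8 | 0.45 | 13% | 13% | 2.2% |

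The geometric-mean column can be checked directly as Φ(−log10(2) × √9 / d): Φ(−3.01) = 0.0013 for d = 0.30 and Φ(−2.01) = 0.022 for d = 0.45. With the same subjects at both visits, the ratio of geometric means equals the geometric mean of the within-subject fold changes.

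If all the variability of change is placed at the later visit, the arithmetic mean rises in 7-26% of trials and the median in 4-13%, with the geometric mean unchanged. That setting is less fair to the arithmetic mean, because its expected value then falls only to 0.64 (d = 0.30) or 0.86 (d = 0.45) of baseline, not to one half.

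**The case against.** The case for leaving the text alone is substantial.

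- The SAP 6.1 default already includes the median, quartiles, minimum and maximum. With three subjects, the minimum, median and maximum are the three values, so a high titre is plain to see. This stands.
- Pre-dose and later visits from both studies appear in the same tables, and listings are planned. With at most 12 subjects a reader can derive each trajectory. This stands, but it leaves the reader to compute the quantity that the endpoint is about.
- The SAP does not say whether titres are treated as continuous or as categories. The arithmetic mean is the natural reading, not an explicit instruction. This stands.
- The table shells are kept separately (SAP section 8) and may already contain more. This cannot be settled from the documents.
- Protocol 12.6 is as brief as SAP 6.9.7, so the reading of protocol 12.4.4 with Table 2 is supporting evidence and not proof of a departure. This stands.

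Two stronger readings are tempting. A reader might infer that one high titre dominates every column. The planned table does not support that: the median and quartiles resist a single value, and in the 9- and 12-subject columns the highest subject's median share stays below half even at the wider assumed spread. A reader might also infer that the raw scale wastes power. The study plans no hypothesis test and no interval for this endpoint, and "The sample size is not based on a power calculation", so a power comparison would describe an analysis that is not in the plan.

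**Conclusion.** The gap is real and minor. SAP 6.9.7 plans no titre-appropriate summary and no within-subject change for an endpoint worded as development over time, although protocol 12.4.4 with Table 2 points to change from baseline.

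In the 3-subject columns the mean and SE largely reflect the highest titre if the spread is wide (median share 61-73% at an assumed log10 SD of 0.5-0.8), and less so if it is narrow. At n = 12 the share is 30-44%. The median and listings limit the harm, but a by-visit median can still point the wrong way: 4-13% of simulated trials at n = 9 under a true halving, against 0.1-2.2% for the geometric mean.

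Every one of these percentages rests on assumed spreads and on lognormal titres. The absence of a planned within-subject change does not. Because the endpoint is tertiary and descriptive, this is a change to consider, not a condition for a sound analysis.

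**What to change.** Amend SAP 6.9.7 and the matching table shells:

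1. For results reported as a titre or concentration, add the geometric mean and geometric SD (log10 scale) by visit, alongside the median and range.
2. Add within-subject fold change from the pre-dose baseline of SAP 4.1, as a geometric mean ratio with the individual values shown.
3. Present both by cohort, for Cohorts 2-4 combined and overall.
4. For any qualitative result, give the number of subjects newly positive since baseline.
5. State that the X/2 rule of SAP 6.9.3 for values below the quantification limit extends to these assays. It is written there for laboratory measurements and SAP 6.9.7 does not invoke it.

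The cost is a few lines of text and revised shells, with no new data or visits. The one small downside is that a below-limit rule must be fixed before logs are taken, and fold changes for subjects near the limit will depend on it.

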6.9.8. Cell-mediated Immune Response to AAV8 and G6Pase

The presence of T cells specific for AAV8 and G6Pase will be determined by an enzyme-linked immunospot (ELISPOT) assay.

Antigen specific response (ASR) for a subject at a visit will be calculated as $M1 - S1 - (M2 + [2 \times S2])$ where M1 and S1 are antigen specific mean spots count and standard deviation and M2 and S2 are medium mean spots count and standard deviation, respectively, at that visit. ASR will be summarized by visit.

ASR will be further categorized as None ($ASR \leq 3$ or $M1 \leq 10$), Low ($ASR > 3$ and ≤ 50), Medium ($ASR > 50$ and ≤ 100) or High ($ASR > 100$) and will be summarized by visit. ASR is not applicable (N/A) if PHA mean spots count is < 100 or Medium mean spots count is greater than 20% of the PHA mean spots count.

Individual subject profiles for ALT and steroid use will be plotted with ASR. Analyses will be repeated by excluding samples with poor PHA response (i.e., lower than expected PHA stimulation response e.g., the result is not “too numerous to count”). Listings of ELISPOT data will be provided. Data from both studies 401GSDIA01 and 401GSDIA02 will be included in this analysis.

6.9.9. Vector Shedding

Blood, saliva, urine, and stool samples for vector shedding were to be collected for subjects who did not demonstrate clearance in Study 401GSDIA01. There was no subject who did not demonstrate clearance in Study 401GSDIA01 study, hence no vector shedding data is expected to be collected in Study 401GSDIA02. A listing of available vector shedding data in Study 401GSDIA02 will be provided if any data is collected.

6.10. Impact of COVID-19 on Study Participation

The study has been ongoing during the COVID-19 pandemic. To capture the impact of COVID-19 on subjects' study participation, the study eCRFs and eCRF completion guidelines were modified during the study as per the regulatory guidance to capture COVID-19 related AEs and reasons for study discontinuation, missed/delayed visits, and missed assessments due to COVID-19 as "COVID-19 related reason". Study data listings will include this information e.g., listing of AEs will include any AEs related to COVID-19 and listing of protocol deviations will include deviations related to missed visits and missed assessments due to COVID-19. These listings will be used to assess any potential impact of COVID-19 on subjects' study participation.

7. CHANGES TO ANALYSIS SPECIFIED IN PROTOCOL

Not applicable.

8. LIST OF PLANNED TABLES AND FIGURES

List of planned tables, figures, and listings will be included in the shell document which will be maintained separately.

10. APPENDICES

APPENDIX 1. HANDLING OF MISSING AND INCOMPLETE DATA

Missing clinical outcome data can occur for multiple reasons, including missed subject visits and scales or measures with missing item scores. Missing and incomplete data will be identified through the data quality review plan for investigation, and possible resolution, by Data Management prior to the study database lock or snapshot.

Unless specified otherwise, only the observed data (not imputed data) will be presented in listings.

Missing Medical History Related Dates

- If only day is missing, impute 1.
- If month is missing, impute January 1st.
- If year is missing, then no imputation will be done; the date will be missing.

If the imputed date is earlier than the birth date, then the birth date will be used.

Missing Birth Dates

To impute missing birth date, the following rules will be applied:

- If day is missing, impute 15.
- If month is missing, impute June.
- If year is missing, then no imputation will be done; the date will be missing.

If the imputed date is later than any study visit date/observed adverse event start date/ observed concomitant medication start date, then earliest available visit date/adverse event start date/ concomitant medication start date will be used without changing observed information.

Missing Date Imputation for Adverse Events and Concomitant Medications

The following conventions will be used to impute missing portions of dates for adverse events and concomitant medications. Note that the imputed values outlined here may not always provide the most conservative date.

Missing Start Dates

- If the day is unknown, then:
 - If the month and year match the month and year of the Visit 1 (Week 52) date, then impute the day of the Visit 1 (Week 52) date.
 - Otherwise, assign the first day of the month.
- If the month is unknown, then:
 - If the year matches the year of the Visit 1 (Week 52) date, then impute the month and day of the Visit 1 (Week 52) date.
 - Otherwise, assign ‘January 1st’

- If the year is unknown, then the date will not be imputed and will be assigned a missing value.

If the imputed date is earlier than birth date, then birth date will be used. If the imputed start date is later than the end date, then the start date will be set as the same date as the end date.

Missing Stop Dates and not ongoing

- If the day is unknown, then assign the last day of the month.
- If the month is unknown, then assign ‘December.’
- If the year is unknown, then the date will not be imputed and will be assigned a missing value, and the event will be considered ongoing. If the AE has been recorded as resolved/recovered, all efforts should be made to obtain the date from the Investigator.

If the resulting end date is after the date of study completion / discontinuation/ data cutoff, set the imputed end date as close to the date of study completion / discontinuation/ data cutoff as possible without overwritten existing information.

If the year is missing for the start date and stop date (observed or imputed) is on or after the Visit 1 (Week 52) date or event is ongoing, the start date will be imputed as the Visit 1 (Week 52) date.

Missing Causal Relationship to Investigational Product for Adverse Events

If the causal relationship to DTX401 is missing for an AE, a causality of “related” will be assigned. The imputed values for causal relationship to DTX401 will be used for the summary; the values will be shown as missing in the data listings.

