6.9.1. Adverse Events

Adverse events will be coded by system organ class (SOC) and preferred term (PT) using the current version of Medical Dictionary for Regulatory Activities.

An AE (classified by preferred term) will be considered a treatment emergent adverse event (TEAE) if it occurred on or after the first dose of IP.

AEs from both studies 401GSDIA01 and 401GSDIA02 will be combined for this analysis. Further, AEs from Study 401GSDIA02 will also be summarized separately.

Subject incidence of TEAEs will be tabulated as the follows. The number of events will also be included.:

- Summary of TEAEs
- TEAEs by SOC and PT
- Related TEAEs by SOC and PT

- Serious Related TEAEs by SOC and PT
- Grade 3 or 4 TEAEs by SOC and PT
- Fatal TEAEs by SOC and PT
- TEAEs leading to discontinuation of study by SOC and PT
- TEAEs by PT
- TEAEs by PT and greatest severity
- TEAEs by their time of occurrence (<1, 1-2, 2-3, 3-4, 4-5, 5-6 years since the IP administration)

The severity will be based on the most current version of CTCAE. If an AE cannot be graded based on CTCAE, the investigator will assign a severity based on 1 = mild, 2 = moderate, 3 = severe, 4 = life threatening, and 5 = death. Detailed listings for all AEs, serious TEAEs, TEAEs leading to the discontinuation of study, and death will also be generated.

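### SAP Appendix 1 does not tie partial adverse-event start dates to the DTX401 dose date, so a post-dose event from Study 401GSDIA01 can be imputed before dosing and drop out of the pooled TEAE tables

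*SAP*

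**What the plan says.** SAP 6.9.1 combines the adverse events of both studies, and also summarizes those of Study 401GSDIA02 separately. An event "will be considered a treatment emergent adverse event (TEAE) if it occurred on or after the first dose of IP". The single dose was given in Study 401GSDIA01 (SAP 3.2), about 52 weeks before Visit 1 of this study.

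SAP Appendix 1 gives one set of start-date rules for adverse events and concomitant medications, and does not limit them to one study:

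- **Day unknown.** Use the Visit 1 day if month and year match Visit 1. "Otherwise, assign the first day of the month".
- **Month unknown.** Use the Visit 1 date if the year matches Visit 1. "Otherwise, assign ‘January 1st".
- **Year unknown.** The start stays missing, unless the "stop date (observed or imputed) is on or after the Visit 1 (Week 52) date or event is ongoing"; it is then set to the Visit 1 date.
- **Limits.** "If the imputed date is earlier than birth date, then birth date will be used". If the imputed start falls after the end date, "then the start date will be set as the same date as the end date".

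The appendix adds two general remarks: "Missing and incomplete data will be identified through the data quality review plan for investigation, and possible resolution, by Data Management", and "Note that the imputed values outlined here may not always provide the most conservative date".

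**The concern.** The dose date decides whether an event is treatment-emergent, yet no start-date rule uses it. Visit 1 is a sensible anchor for events collected in Study 401GSDIA02, which begin at consent about a year after dosing. It is the wrong anchor for first-year events, whose partial dates need to be placed relative to dosing.

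The primary endpoint is the incidence of AEs and SAEs, and the pooled incidence tables count TEAEs. An event imputed before dosing leaves those tables, including the breakdown by year since dosing and, for a hepatic event, the AESI table. If serious, it also leaves the serious-TEAE listing. It stays in the all-AE listing with its observed partial date, but a reader of the tables would not see why it is absent. Study 401GSDIA01 enrolled three subjects per cohort (Protocol 5.4). If all three are in the analysis set and the lost event was a subject's only one in a table row, that cohort's incidence falls by 1/3, or 33 percentage points.

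**Working it through.** The plan states no figure on this point, so the check applies the Appendix 1 rules to truly post-dose events.

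**Example (assumed dates).** Dose 20 March 2019; Visit 1 at +364 days is 18 March 2020. An event on 25 March 2019 recorded as March 2019 becomes 1 March 2019. Recorded as 2019 only, it becomes 1 January 2019. Both dates precede dosing. The birth-date floor does not apply, and the end-date rule can only move a start earlier.

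**Inputs.** Visit 1 = dose + 364 days (Week 52, window ±7 days, Protocol Table 1). Assumed, because no dose dates are given: every dose date of a 365-day year, and every onset day from 0 to 363, equally likely. Pairs: 365 × 364 = 132,860.

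**Day unknown.** In a month of L days, dosing on day d ≥ 2 leaves L − d + 1 onset days in that month, all imputed to the 1st. Summed over d this is L(L − 1)/2 pairs.

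- Year: 7 × 465 + 4 × 435 + 378 = 5,373.
- Share of all pairs: 5,373/132,860 = 4.0%.
- All pairs in the dosing month: 7 × 496 + 4 × 465 + 406 = 5,738. Share: 5,373/5,738 = 93.6%. The exceptions are doses on the 1st.

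**Month unknown.** Dosing on day k ≥ 2 of the year leaves 366 − k onset days in that calendar year, all imputed to January 1st.

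- Sum over k = 2 to 365: 364 × 365/2 = 66,430.
- Share of all pairs: 66,430/132,860 = 50.0%.
- Within the dosing calendar year: 66,430/(66,430 + 364) = 66,430/66,794 = 99.5%. The exception is a dose on January 1st.

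**By 91-day quarter after dosing** (365 × 91 = 33,215 pairs each):

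| Quarter | Day unknown | Month unknown |
|---|---|---|
| 1 | 5,373 (16.2%) | 29,029 (87.4%) |
| 2 | 0 | 20,748 (62.5%) |
| 3 | 0 | 12,467 (37.5%) |
| 4 | 0 | 4,186 (12.6%) |

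**Visit 1 window.**

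- Dose + 357 days: 5,373/130,305 = 4.1% and 63,903/130,305 = 49.0%.
- Dose + 371 days: 5,373/135,415 = 4.0% and 66,430/135,415 = 49.1%.

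**Early clustering.** With assumed weights exp(−t/m) and m = 180, 90 or 60 days, the day-unknown share is 8.9%, 14.9% or 21.0%, and the month-unknown share 65.8%, 77.0% or 83.7%. These show direction only; the documents give no onset distribution.

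**Other branches.** The Visit 1 branch never gave a pre-dose date. An event with no start year that stopped after dosing but before Visit 1 keeps a missing start, so its treatment-emergent status is undefined. This case is remote.

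**With a dose-date anchor:** 0 of 132,860 for both types.

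**The case against.** The strongest objection is scope. Every study anchor in Appendix 1 is Visit 1, which is entry to Study 401GSDIA02, so the rules may have been written for that study's records only. The Protocol synopsis says this study's safety database holds its own results only. Study 401GSDIA01 was completed in November 2022 and has its own clinical study report, so its partial dates may already have been imputed under rules not available here. That is possible, but no text limits Appendix 1 in this way, and SAP 6.1 and 6.9.1 require the pooling. The fix below covers this case.

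The SAP also does not say outright that the imputed date sets the TEAE flag. That link is inferred, though it is hard to see another main use, since listings show observed data by default.

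Three points stand:

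- Every share above is conditional on a partial date existing. With up to 12 subjects and Data Management review, there may be none. That review promises only possible resolution, however, and imputation rules exist for dates that stay partial.
- The larger shares need an event whose month is unknown. For any one subject, that branch runs only from dosing to 31 December of the dosing year.
- The study is descriptive, the all-AE listing is complete, and the separate Study 401GSDIA02 summary is untouched.

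The warning that imputed dates may not be the most conservative admits the weakness without correcting it. It also sits oddly beside the rule in the same appendix that treats missing causality as related.

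**Conclusion.** The concern holds. Followed as written, Appendix 1 dates a post-dose Study 401GSDIA01 event before dosing in nearly every case where the day is unknown in the dosing month (93.6%) or the month is unknown in the dosing calendar year (99.5%). Over the whole first year the shares are 4.0% and 50.0%, and they are highest soon after dosing. These figures assume evenly spread dose and onset dates, Visit 1 at dose + 364 days, and that the imputed date sets the TEAE flag. The absolute number of events is unknown and may be zero. Because the gap is in a stated rule that feeds the primary-endpoint tables and is cheap to close, it should be fixed.

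**What to change.** In SAP Appendix 1, for adverse events collected in Study 401GSDIA01:

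- If the known parts of the start date match the month and year of the dose date (or the year, when only the year is known), impute the dose date, unless the stop date or other known parts show onset before dosing.
- If the start year is missing and the event is ongoing or stopped on or after dosing, impute the dose date.
- Keep the Visit 1 anchor for adverse events collected in Study 401GSDIA02.

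If Study 401GSDIA01 dates are carried over as already imputed in that study, say so in Appendix 1 instead.

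The cost is a few lines of text and programming, with no new data. The downside is that some pre-dose events with partial dates would count as TEAEs, unless shown to have ended or begun before dosing. If events were collected for 14 days before dosing (assumed; not given), this would be up to 3,850/5,110 = 75.3% of day-unknown and 5,005/5,110 = 97.9% of month-unknown pre-dose events. For 60 days it would be up to 5,373/21,900 = 24.5% and 20,070/21,900 = 91.6%. The number of such events is also unknown and may be zero. The error is towards counting an event in a safety table rather than losing one.
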